6.4 Inclusions of Women and Minorities

Both Men and Women and all minorities are eligible for participation.

6.5 Multicenter Trial Management

6.5.1 Personnel

At each site, personnel dedicated to this protocol will be:

- A study PI
- A research coordinator
- A data manager

In addition, Georgetown University's Multicenter Project Management Office will oversee the conduct of the trial at Lombardi-Georgetown and additional sites. Georgetown University's Multicenter Project Management Office will be the main point of contact for [name] and the other site PIs for any study related concerns including data management and regulatory.

6.5.2 Patient Enrollment

Enrollment at the sites will be competitive. If a patient is consented and being screened for enrollment, the local research coordinator must send an email within 24 hours containing the Patient registration form to the local PI, [name], Georgetown University's Multicenter Project Management Office and Erytech. If a patient is successfully screened, the local research coordinator must send all supporting documentation to Georgetown University's Multicenter Project Management office by secure email to confirm eligibility. Patients should not start therapy until [name] and Georgetown University's Multicenter Project Management office have reviewed the patient's records and confirmed that the patient is indeed eligible for enrollment.

6.5.3 Data Collection and Management

Patient data will be entered into the on-line accessible database. This database is housed at Lombardi-Georgetown but is accessible anywhere there is internet access. The data manager and research coordinator at each site will attend an on-line training session so that they may learn how to enroll data into the data base. All screening data should be entered prior to starting therapy, and all ongoing patient data should be entered within 10 business days of each patient visit.

6.5.4 Conference Calls

A weekly conference call will be held between Lombardi-Georgetown and the other sites to review patient enrollment, toxicity, and response assessment.

6.5.5 Trial Auditing

Georgetown University's Multicenter Project Management Office will arrange all primary source documents for the patients to be audited. This will include collecting copies of the primary source data for any patients treated at other sites.

7 Study Procedures

7.1 Screening and Enrollment

For patients being considered for enrollment outside of Georgetown-Lombardi, all primary source documentation should be sent to Georgetown University's Multicenter Project Management Office, and the principal investigator, [name], for review and approval. Patients must be approved for accrual prior to starting study medications. Patient IDs will be assigned at the time of registration.

Informed consent must be obtained prior to the performance of study related evaluations.

Within 21 days prior to study entry subjects will undergo the following evaluations:

- o Demographics, medical history, and concomitant medications
- o A physical exam, height, and weight measurements
- Vital signs including temperature blood pressure and heart rate
- o A 12-lead ECG will be obtained
- Subject performed status will be assessed via the ECOG scale
- Samples will be collected for serum chemistry hematology, coagulation, and CA-19-9
- Irregular antibody screening test (IAST)
- Blood phenotype
- Radiographic assessments will be obtained during screening and then repeated every 8 weeks from the time of enrollment until disease progression or death

7.2 Study Day -8 to Day -5

The following procedures will be performed at least 5 days prior to Cycle 1 Day 1:

• Prescription with current weight

7.3 Study Day 1

The following procedures will be performed:

- Physical examination
- Vital signs including temperature blood pressure and heart rate
- Subject performed status will be assessed via the ECOG scale
- o 12-lead ECG
- Pre-Eryaspase dose complete compatibility test
- Irregular antibody screening test (IAST)
- Samples will be collected for serum chemistry hematology, coagulation, and CA 19-9
- For all women of childbearing potential, a urine pregnancy test will be administered
- Eryaspase Administration
- FOLFIRINOX Administration

7.4 Study Day 8

The following procedures will be performed:

- Physical examination
- o Vital signs including temperature blood pressure and heart rate
- \circ Subject performed status will be assessed via the ECOG scale
- o All adverse events will be recorded

7.5 Study Day 15

The following procedures will be performed:

- Physical examination
- o Vital signs including temperature blood pressure and heart rate
- \circ Subject performed status will be assessed via the ECOG scale
- All adverse events will be recorded
- o 12-lead ECG
- Pre-Eryaspase dose complete compatibility test
- Irregular antibody screening test (IAST)
- Samples will be collected for serum chemistry hematology, coagulation, and Ca 19-9
- For all women of childbearing potential, a urine pregnancy test will be administered
- Eryaspase Administration
- FOLFIRINOX Administration

7.6 Study Day 22

The following procedures will be performed:

- Physical examination
- \circ Vital signs including temperature blood pressure and heart rate
- \circ Subject performed status will be assessed via the ECOG scale
- o All adverse events will be recorded

7.7 Study Day 1 and Day 15 of each subsequent cycle

The following procedures will be performed:

- Physical examination
- o Vital signs including temperature blood pressure and heart rate
- Subject performed status will be assessed via the ECOG scale
- All adverse events will be recorded
- o Pre-Eryaspase dose complete compatibility test
- o Irregular antibody screening test (IAST)
- Samples will be collected for serum chemistry hematology, coagulation, and CA19-9
- For all women of childbearing potential, a urine pregnancy test will be administered
- Eryaspase Administration
- FOLFIRINOX Administration

7.8 End of Treatment/Safety Follow-up

Subjects will complete an end of treatment (EOT) evaluation 4 weeks (+/- 7 days) after the last day of treatment on study or after tumor progression is documented. In addition, a positive urine test must be confirmed by a serum pregnancy test.

Survival follow up will be conducted by phone, visit, or medical records review every 8 weeks $(\pm 1 \text{ week})$ from end of treatment visit until patient's death, loss to follow up, or study closure. Subsequent anti-cancer treatment should be collected during this follow up.

8 Study Assessment

8.1 Efficacy Assessments

8.1.1 Tumor Assessment

Methods of evaluation of Measurable Disease

Clinical lesions: Clinical lesions will only be considered measurable when they are superficial (e.g., skin nodules and palpable lymph nodes) and 10 mm diameter as assessed using calipers (e.g., skin nodules). In the case of skin lesions, documentation by color photography, including a ruler estimating the size of the lesion, is recommended.

Conventional CT and MRI: These guidelines have defined measurability of lesions on CT scans based on the assumption that CT slice thickness is 5 mm or less. If CT scans have slicing thickness greater than 5 mm, the minimum size for a measurable lesion should be twice the slice thickness. MRI is also acceptable in certain situations (e.g. for body scans).

Use of **MRI** remains a complex issue. MRI has excellent contrast, spatial, and temporal resolution; however, there are many image acquisition variables involved in MRI, which greatly impact image quality, lesion conspicuity, and measurement. Furthermore, the availability of MRI is variable globally. As with CT, if an MRI is performed, the technical specifications of the scanning sequences used should be optimized for the evaluation of the type and site of disease. Furthermore, as with CT, the modality used at follow up should be the same as was used at baseline and the lesions should be measured/assessed on the same pulse sequence. It is beyond the scope of the RECIST guidelines to prescribe specific MRI pulse sequence parameters for all scanners, body parts and diseases. Ideally, the same type of scanner should be used and the image acquisition protocol should be followed as closely as possible to prior scans. Body scans should be performed with breath hold scanning techniques, if possible.

8.2 Safety Assessments

8.2.1 Physical Examinations, Vital Signs, and ECGs

A physical examination will be performed during screening, Cycle 1 Days 1, 8, 15, and 22, and Day 1 and Day 15 on all subsequent cycles.

Vital signs will be measured at all study visits. Blood pressure, pulse rate, and body temperature will be measured in accordance with the study site's standard operating procedures. Body weight and height will be measured at screening. Body height will be performed only at the screening period, and body weight will be measured at all visits.

12-Lead ECGs will be acquired during the Screening period, and on Day 1 (pre-dose), Day 15 (pre-dose) of Cycle 1. The ECG recordings will be reviewed for any evidence of abnormalities. In particular, any evidence of QT/QTcF prolongation will be recorded as an adverse event.

8.2.2 Clinical Laboratory Assessments

The following tests will be performed at the local laboratories at the visits identified in the Time and Events tables.

- Hematology: hemoglobin, hematocrit, red blood cell (RBC) count, white blood cell (WBC) count with differential, platelet count, mean cell hemoglobin (MCH), mean cell hemoglobin concentration (MCHC), mean corpuscular volume, reticulocytes
- Serum Chemistry: liver panel (total and direct bilirubin, AST, ALT), GGT, renal panel (BUN, creatinine), albumin, sodium, potassium, magnesium, bicarbonate, chloride, calcium, inorganic phosphorus, glucose, total protein, alkaline phosphatase,, amylase, and lipase.

- **Coagulation:** Coagulation profile, plasma antithrombin III, fibrinogen, D-dimer, the international normalized ratio (INR), and partial thromboplastin time (PTT).
- Pregnancy test (for all women of childbearing potential): Serum or Urine β HCG test
- Tumor Marker: CA19-9
- Complete compatibility testing: To be performed prior to Eryaspase administration by the blood bank at the Institution. If not compatible, eryaspase should NOT be administered and the sponsor notified immediately. Depending on the individual circumstances the patient may receive chemotherapy alone and resume eryaspase at the next dose or delay dose for Erytech to remanufacture and ship the new bag of eryaspase. If incompatibility persists the patient will NOT receive further eryaspase, but can continue chemotherapy alone.

8.3 Regulatory and Reporting Requirements

8.3.1 Adverse Events (AE)

Adverse events are defined as any untoward medical occurrence in a subject participating in a clinical trial who is administered an investigational product, at any dose; the adverse event does not necessarily have to have a causal relationship with this product. An adverse event could, therefore, be any unfavorable and/or unintended sign (including abnormal laboratory findings), symptom, or disease temporally associated with the use of an investigational product, whether or not considered related to the investigational product. This definition includes intercurrent illnesses or injuries, and exacerbation of pre-existing conditions.

All adverse events occurring in subjects who have received the treatment will be recorded on the CRF and will be reported in accordance with regulatory requirements. Adverse events reported prior to the commencement of administration of study medication will be considered pretreatment events. All adverse events will be monitored until resolution or, if the AE is determined to be chronic, until a cause is identified. To the extent possible, any adverse events that are deemed to study drug-related and are ongoing at End of Treatment will be followed up to resolution or until a determination is made that the unresolved event is stable. If an adverse event remains unresolved at the conclusion of the study, a clinical assessment will be made by the Investigator and the Sponsor's Medical Monitor whether continued follow-up of the adverse event is warranted.

Laboratory abnormalities and changes in vital signs are considered to be adverse events only if they result in discontinuation from the study, necessitate therapeutic medical intervention, and/or if the investigator considers them to be adverse events.

An **elective surgery/procedure** scheduled to occur during a study will not be considered an adverse event if the surgery/procedure is being performed for a pre-existing condition and the surgery/procedure has been pre planned prior to study entry. However, if the pre-existing condition deteriorates unexpectedly during the study (e.g.,

surgery performed earlier than planned), then the deterioration of the condition for which the elective surgery/procedure is being done will be considered an adverse event.

8.3.1.1 Grading Adverse Events

The descriptions and grading scales found in the revised NCI Common Terminology Criteria for Adverse Events (CTCAE) version 5.0 will be utilized for all toxicity reporting. A copy of the CTCAE version 5.0 can be downloaded from the CTEP website. https://ctep.cancer.gov/protocoldevelopment/electronic_applications/docs/CTCAE_v5_Quick_Reference_5x7.pdf

For AEs not listed, the following scale will be used:

- Mild (Grade 1): no limitation of usual activities
- Moderate (Grade 2): some limitation of usual activities
- Severe (Grade 3): inability to carry out usual activities
- Life-threatening (Grade 4): an immediate risk of death
- Death (Grade 5)

8.3.2Unanticipated Problems

An unanticipated problem is defined as:

- **Unexpected** (in terms of nature, severity or frequency) given (a) the research procedures that are described in the protocol-related documents, such as the IRB-approved research protocol and informed consent document; and (b) the characteristics of the subject population being studied;
- **Related or possibly related** to participation in the research (in this guidance document, possibly related means there is a reasonable possibility that the incident, experience, or outcome may have been caused by the procedures involved in the research); and
- **Suggests** that the research places subjects or others at a greater risk of harm (including physical, psychological, economic, or social harm) than was previously known or recognized.

Since it is anticipated that there will be deaths due to pancreatic cancer progression in this study, death will not necessarily be considered unexpected in this study.

8.3.3 Relationship to Study Drug

The investigator will use the following definitions to assess the relationship of the adverse event to the use of study drug:

Related: A causal relationship between the medicinal product (and/or study procedures) and AE is a reasonable possibility. For example, the occurrence of the AE cannot be explained by other causative factors. The AE, however, can be explained by pharmacological effect of the medicinal product such as a similar event having been reported previously, alteration of the dose effect, or the timing or seriousness of the AE, etc. Positive re-challenge/de-challenge is supportive.

Not Related: A causal relationship between the medicinal product (and/or study procedures) and AE is not a reasonable possibility: there is no temporal relationship between the medicinal product and event, or an alternative etiology is more reasonable.

For every adverse event, the investigator must attribute whether the adverse event was due to study medication, or other causes. If an investigator's opinion of probably not or not related to study drug(s) is given, an "other" cause of event must be provided by the investigator for the adverse event.

8.3.4Serious adverse event (SAE)

A Serious Adverse event (SAE) is defined as any untoward medical occurrence that at any dose:

- Results in death
- Is life-threatening (i.e., the patient was, in the opinion of the Investigator or Sponsor, at immediate risk of death from the event as it occurred)
- Requires or prolongs hospitalization (unless planned for observation, protocol compliance, elective procedures, social reasons). This does not include an emergency room visit or admission to an outpatient facility.
- Results in persistent or significant disability or incapacity
- Is a congenital anomaly or birth defect
- Is an important and significant medical event that, based on appropriate medical judgment, may jeopardize the patient and/or may require medical or surgical intervention to prevent one of the other outcomes defining serious.

Disease progression is an efficacy criterion and is therefore not considered an AE or SAE (even if fatal). Disease progression should be documented. If AEs/SAEs occur in relation to disease progression that are not consistent with the natural progression of the patient's disease, these AEs/SAEs must be reported per AE/SAE reporting requirements.

For patients enrolled outside of Georgetown University, serious adverse events will also be reported, and all supporting documentation emailed to Georgetown University's Multicenter Project Management Office and to the study PI, [name], within 24 hours.

If an adverse event meets any of the following criteria, it will be reported to the Georgetown DSMC as a SAE by the Sponsor-Investigator or designee per DSMC reporting guidelines.

SAEs will be collected and recorded from the time the patient receives the first dose in the study until he/she completes the End of Treatment visit. SAEs brought to the attention of the investigator at any time after cessation of the study drugs and considered by the investigator to be related or possibly related to the study drugs must be reported to the Sponsor-Investigator and Multicenter Project Management Office, if and when they occur.

8.3.5Serious Unexpected Suspected Adverse Reaction

A serious unexpected suspected adverse reaction is defined as an unexpected serious adverse event where there is a reasonable possibility that the drug caused the serious

Version 2.1, 16 March 2022

adverse event. For the purposes of expedited safety reporting, "reasonable possibility" means there is evidence to suggest a causal relationship between the drug and the adverse event. Suspected adverse reaction implies a lesser degree of certainty about causality than adverse reaction, which means any adverse event caused by a drug.

8.3.6 Stopping Criteria

We will follow guidelines for early termination of the study per the 3+3 study design.

8.3.8 Reporting of Pregnancy

In cases of pregnancy or suspected pregnancy, the patient is to be discontinued immediately (within 24 hours) from the study and the female patient should be referred to an obstetriciangynecologist, preferably one experienced in reproductive toxicity for further evaluation and counseling. Pregnancy, suspected pregnancy, a positive pregnancy test and pregnancy outcomes must be reported to the study PI, and the Multicenter Project Management Office. If the pregnancy results in spontaneous abortion or stillbirth, the event should be reported as an SAE. If there are any abnormal outcomes that meet the serious criteria, it must be reported as an SAE. Please follow the SAE reporting instructions. Pregnancy outcomes must be collected for the female partners of any males who took study drug in this study. Pregnancy of the patient's partner is not considered to be an AE. Consent to report information regarding these pregnancy outcomes should be obtained from the female partner.

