[11] For patients of childbearing potential, serum pregnancy test to be performed during the screening period and at End of Treatment and urine/serum pregnancy test to be performed prior to dosing of any chemotherapy agent
[13] Survival follow to be conducted by phone, visit, or medical records review every 8 weeks (± 1 week) from end of treatment visit until patient's death, loss to follow up, or study closure. Subsequent therapy should be collected during this follow up.

Additional lab tests may be required (e.g., weekly monitoring per standard practice or label requirements should be followed) and should be reported if clinically significant

[14] SAEs are not required to be reported until after they received the first dose.

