D Diarrhea		Patients should be instructed in the use of loperamide as treatment for diarrhea. Patient should not be retreated with irinotecan until recovery from diarrhea, without loperamide for at least 24 hours, has occurred
Toxicity Grade		
2	Consider holding, but can treat per Investigator discretion.	
	1st occurrenc	e: Reduce irinotecan by 1 dose level
3-4	2nd occurrent FU dose by 1	ce: Reduce oxaliplatin dose by 1 dose level and 5- dose level
	3rd occurrenc	e: Discontinue all protocol treatment

Table 4E

E Mucositis			
Toxicity Grade	5-F	FU	Oxaliplatin
2	Hold tre	eatment	Hold treatment
	until resolution	n to ≤ Grade 1,	until resolution to ≤ Grade 1,
	Continue at sa	ame dose level	Continue at same dose level
3-4	Hold tre	eatment	Hold treatment
	until resolution	n to ≤ Grade 1,	until resolution to ≤ Grade 1,
	Continue at ne	ext lower dose	Continue at next lowest dose
	lev	vel	level

Table 4F

F Oxaliplatin related neuropathy		Paresthesia or peripheral sensory neuropathy	
Toxicity Grade	Duration of toxicity 1–7 days	Duration of toxicity more than 7 day	Persistent (duration of toxicity more than 14 days)
2	No dose modification	No dose modification	Next lowest dose level for oxaliplatin
3	Next lowest dose level for oxaliplatin	Next lowest dose level for oxaliplatin	Discontinue
4	Discontinue	Discontinue	Discontinue

Table 4G

G		
Palmar-plantar erythrodysesthesia syndrome		
Toxicity Grade 2	Consider holding	, but can treat per Investigator discretion.
Toxicity Grade 3-4	Rec	luce 5–5-FU by 1 dose level

5.7 Discontinuation of Eryaspase

- DLT during dose escalation
- Study completion
- Patient withdraws from the study for any reason, including withdraws consent.
- Progressive disease
- Declared discontinuation due to missed Eryaspase doses.

5.8 Duration of therapy

If at any time the constraints of this protocol are considered to be detrimental to the patient's health and/or the patient no longer wishes to continue protocol therapy, the protocol therapy should be discontinued and the reason(s) for discontinuation documented in the case report forms.

Version 2.1, 16 March 2022

In the absence of treatment delays due to adverse events, treatment may continue for a total of 12 treatments of FOLFIRINOX (approximately 6 months) or until one of the following criteria applies:

- Documented and confirmed disease progression
- Death

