- Adverse event(s) that, in the judgment of the investigator, may cause severe or permanent harm or which rule out the continuation of study drug
- General or specific changes in the patient's condition render the patient unacceptable for further treatment in the judgment of the investigator
- Suspected pregnancy
- Serious non-compliance with the study protocol
- Lost to follow-up
- Patient withdraws consent
- Investigator removes the patient from the study
- The Sponsor-Investigator or Georgetown decides to close the study

After 12 treatments of FOLFIRINOX, patients have the option to continue FOLFIRINOX plus Eryaspase or can transition to FOLFIRI (dropping Oxaliplatin) plus Eryaspase or 5-FU (dropping Irinotecan and Oxaliplatin) plus Eryaspase, at the investigator's discretion.

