5.10 Women of childbearing potential

Women of childbearing potential (women with regular menses, women with amenorrhea, women with irregular cycles, women using a contraceptive method that precludes withdrawal, or women who have had a tubal ligation) are required to have a negative serum pregnancy test within 14 days prior to the first dose of Eryaspase.

Female and male patients (along with their female partners) are required to use two forms of acceptable contraception, including one barrier method, during participation in the study and for 1 month following the last dose of Eryaspase.

If a patient is suspected to be pregnant, Eryaspase should be immediately discontinued. In addition, a positive urine test must be confirmed by a serum pregnancy test. If it is confirmed that the patient is not pregnant, the patient may resume dosing.

If a female patient or female partner of a male patient becomes pregnant during therapy or within 1 month after the last dose of Eryaspase, the investigator must be notified in order to facilitate outcome follow-up.

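### Sections 5.8 and 8.3.8 end treatment on suspected pregnancy, while 5.10 allows dosing to resume once pregnancy is ruled out; separately, the contraception entry criterion is looser than the on-study rule in 5.10

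*Combined protocol and SAP*

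**What the plan says.** Three sections act on a suspected pregnancy.

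- Section 5.10 (Women of childbearing potential): "If a patient is suspected to be pregnant, Eryaspase should be immediately discontinued". It asks for serum confirmation of a positive urine test and then says: "If it is confirmed that the patient is not pregnant, the patient may resume dosing".
- Section 5.8 (Duration of therapy): "treatment may continue for a total of 12 treatments of FOLFIRINOX (approximately 6 months) or until one of the following criteria applies". One entry in the list that follows is simply "Suspected pregnancy".
- Section 8.3.8 (Reporting of Pregnancy): "In cases of pregnancy or suspected pregnancy, the patient is to be discontinued immediately (within 24 hours) from the study". It adds a reporting duty: "Pregnancy, suspected pregnancy, a positive pregnancy test and pregnancy outcomes must be reported to the study PI".

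Testing precedes every dose. Sections 7.3, 7.5 and 7.7 specify urine: "For all women of childbearing potential, a urine pregnancy test will be administered". Table 1 footnote [11] allows either sample: "urine/serum pregnancy test to be performed prior to dosing of any chemotherapy agent".

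On contraception, 6.1.12 and the synopsis ask women of childbearing potential and men to agree to a hormonal method, a barrier method or abstinence while they take part in the study, and name no period after the last dose. Section 6.1.13 asks men with a partner of childbearing potential for two methods, or a barrier plus another method. Section 5.10 asks male and female patients for two forms, one of them a barrier, during the study and for 1 month after the last Eryaspase dose.

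On the baseline test, 5.10 wants a negative serum result no more than 14 days before first Eryaspase. Section 6.1.11 takes urine or serum with no window, and footnote [11] takes serum at any time in screening.

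**The concern.** All three sections stop treatment on suspicion. They differ on what happens when the suspicion proves wrong. Section 5.10 treats the stop as a hold with a way back. Sections 5.8 and 8.3.8 give no way back, and 8.3.8 takes the patient off the study within 24 hours, so the decision may fall due before a serum result has been acted on. Two sites with the same false-positive urine test could act differently, and each could point to a section of the protocol. The patient at the site that follows 5.8 and 8.3.8 loses Eryaspase and on-study treatment for a reason that a blood test would have removed.

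The scope of the stop differs too. Section 5.10 stops only Eryaspase and is silent on chemotherapy, while 5.8 ends the whole regimen.

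On contraception, a woman can be eligible under 6.1.12 on one method and, from her first dose, fall short of 5.10, while she receives an investigational agent with cytotoxic chemotherapy. A woman relying on abstinence has no stated way to meet 5.10 at all.

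**Working it through.** The plan states no figure on this point, so the check is a comparison of text and a count from the visit schedule.

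**Suspected pregnancy**

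| | 5.10 | 5.8 | 8.3.8 |
|---|---|---|---|
| Trigger | Suspicion | Suspicion | Pregnancy or suspicion |
| What stops | Eryaspase | Protocol treatment | Study participation |
| Confirmation step | Serum test after a positive urine test | None | None |
| If ruled out | May resume | Not addressed | Not addressed |
| Cross-reference | None | None | None |

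A patient who has been taken off the study cannot also resume dosing in it. A site that uses the 5.10 option therefore departs from the plain wording of 8.3.8, and from 5.8 read as a list of end points.

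**What removal forfeits**

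Inputs: 12 planned FOLFIRINOX treatments (5.8), given on days 1 and 15 of a 4-week cycle (5.3), with a pregnancy test before each (7.3, 7.5, 7.7, footnote [11]).

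- Pre-dose tests: 12. Tests after the first dose: 12 − 1 = 11.
- Removal at the test before treatment k forfeits treatments k to 12, which is 13 − k treatments.
- At cycle 1 day 15, k = 2: 13 − 2 = 11 forfeited.
- Before the last treatment, k = 12: 13 − 12 = 1 forfeited.
- Treatment k falls on day 1 + 14(k − 1). For k = 2 this is day 15, and for k = 3 it is day 29. Of the 11 later tests, only the one on cycle 1 day 15 lies in the 28-day DLT period.

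If removal at that visit during escalation counts as withdrawal for a reason other than a DLT, 5.3 calls for a replacement patient, who needs a further 4 weeks of observation.

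The count assumes that the patient would otherwise have completed 12 treatments. Progression or toxicity would make the loss smaller. The option in 5.8 to continue after 12 would make it larger.

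**Contraception**

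| Patient | 6.1.12 | 5.10 |
|---|---|---|
| Woman, hormonal method only | Met | Not met |
| Woman, barrier only | Met | Not met |
| Woman, abstinent | Met | No stated route |
| Woman, hormonal plus barrier | Met | Met |

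For men with a partner of childbearing potential, 6.1.13 already asks for two methods, though not necessarily a barrier. The gap therefore mainly affects women.

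**Baseline test**

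A serum test within 14 days before first Eryaspase satisfies 5.10, 6.1.11 and the screening part of footnote [11] together. A test at the start of screening (21 days in 7.1, up to 28 in 5.1) satisfies the last two but not 5.10.

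**The case against.** The best reply is that 5.10 is the specific rule. It is the only section that says what to do when pregnancy is ruled out, and it uses the language of discontinuation for a stop that it reverses in the same paragraph, so 5.8 could be read the same way. Resumption is permissive, so a site that never restarts complies with all three sections. This much stands: a reader might infer that the instructions are impossible to follow together, and they are not. It does not remove the conflict. The protocol states no order of precedence, and 8.3.8 discontinues the patient from the study, not merely from a drug.

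A reader might also infer that the trigger is wholly undefined, because 8.3.8 lists suspicion and a positive test as separate items to report. That goes too far. Section 5.10 places suspicion, serum confirmation and resumption together, and 7.8 repeats the confirmation step, so an unconfirmed positive urine test is largely implied to be the case in point. It would still help to say so.

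Nor do the documents support the inference that removal ends first-line chemotherapy. Section 9.1.2 describes the FOLFIRINOX components as commercially available. What is lost is Eryaspase and on-study treatment.

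On contraception, 6.1.12 can be read as an entry agreement with 5.10 as the stricter rule on top, and following 5.10 satisfies both. That is fair except for abstinence, which only 6.1.12 recognises. The baseline test timing is likewise a looser rule beside a stricter one, not a contradiction.

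Finally, the event is probably rare, and an average number of lost treatments would carry no evidential weight because nothing in the documents says when such a test would occur. Both points stand.

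**Conclusion.** The inconsistency is real and should be corrected. For a patient whose suspected pregnancy is ruled out, 5.10 permits a restart that 8.3.8, and 5.8 on its plain reading, do not provide for. The entry criterion on contraception is looser than the on-study rule and leaves abstinent women without a way to comply.

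For a patient affected after her first dose, between 1 and 11 of the 12 planned treatments are at stake, assuming that she would otherwise have completed them. The documents give neither a false-positive rate nor the number of women of childbearing potential among the 12 to 19 patients expected, so no frequency can be stated. That it is rare is a judgement.

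A reader might infer a threat to the MTD determination. There is none beyond a possible replacement patient in cycle 1: the 3+3 rule and the planned analyses are unchanged. This is a matter of patient safety and consistent conduct across sites.

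**What to change.** **Suspected pregnancy.** In 5.8 and 8.3.8, replace discontinuation on suspicion with the 5.10 sequence, worded identically in all three places: on suspicion, which includes a positive urine test, hold all study treatment; confirm by serum; resume if negative; discontinue only if pregnancy is confirmed. Extend the hold in 5.10 to chemotherapy. Deleting the restart sentence from 5.10 would also make the sections agree, but it would turn every false positive into a removal.

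**Contraception.** Align 6.1.12, 6.1.13 and the synopsis with 5.10: two forms, one a barrier, during the study and until 1 month after the last Eryaspase dose. Add complete abstinence to 5.10 as an accepted alternative.

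**Minor alignment.** Carry the 14-day serum test of 5.10 into 6.1.11 and footnote [11].

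**Cost.** Amendment wording, consent-form alignment if the form differs, and some retimed screening tests. A hold can delay a dose. If it outlasts the patient-specific bag, whose shelf life the documents do not give, a new one needs a prescription at least 5 working days ahead (9.4.1), about one calendar week. Drawing a serum pregnancy test with the antibody-screening sample, due within 72 hours before each dose (footnote [6]), would avoid most such delays, and footnote [11] already allows serum. In cycle 1, if 5.5 is read as replacing a patient after any delay not caused by toxicity, a held patient would be replaced for the DLT evaluation, which for the DLT count is no worse than removal under 8.3.8.
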